The purpose of this statistical analysis plan (SAP) is to describe the procedures and statistical methodologies that will be used in the analysis and reporting of results for Partner Therapeutics Protocol PTX-001-002.

This document is prepared based on the following documents:

- the study protocol version 2.0 dated 02 December 2020;
- the Case Report Form version 1.7 dated 08 January 2021.

Readers are referred to the final study protocol (and any amendments or addenda), the case report form (CRF), and CRF completion guidelines for details of the study design, conduct and data collection. Any significant changes to these documents in terms of the principal features of the study analyses may result in an SAP amendment; any other changes will be denoted in the Clinical Study Report as changes to the planned analyses.

This SAP must be finalized prior to the locking of the clinical database for this study. The mock summary tables, figures and by subject data listings (TFLs) are provided in a separate document.

5 Study Objectives and Endpoints

5.1 Study Objectives

The aim of the study is to determine if inhaled sargramostim, as an adjunct to institutional SOC, improves clinical outcomes in patients with COVID-19-associated acute hypoxemia.

5.2 Study Endpoints

5.2.1 Primary Endpoints

• Change in oxygenation parameter of P(A-a)O₂ gradient by Day 6 and % of patients who have been intubated by Day 14

5.2.2 Secondary Endpoints

• Change in ordinal scale.

- All cause 28-day mortality.
- Number of patients with treatment-emergent serious adverse events or clinically significant adverse drug reactions (ADRs).
- Survival time and causes of death.
- Time to improvement in oxygenation (PaO₂/FiO₂ ratio, SpO₂/FiO₂ ratio and P(A-a)O₂ gradient).
- Rate of nosocomial infection (as determined by local institution practice).
- Duration of hospitalization.
- Number of patients requiring initiation of mechanical ventilation.
- Duration of invasive and non-invasive ventilation and/or supplemental oxygen.
- Time to normalization of WBC and lymphocytes.

5.2.3 Exploratory Endpoints

- National Early Warning Score (NEWS-2).
- Sequential organ failure assessment (SOFA) scores.
- ROX Index.
- Progression to ARDS.
- Changes on chest X-ray or CT.

6 Study Design

6.1 Study Design Overview

This study is a randomized two-arm open-label study. This Phase 2 study will randomize approximately 120 patients with COVID-19: of which 80 will receive sargramostim + SOC, and 40 patients who will receive SOC alone. Refer to Section 5.1 of the Study Protocol for a more detailed description of the study. Section 1 of the Study Protocol is a schematic of the study design.

6.2 Randomization

Per Section 5.2 of the Study Protocol, randomization will be performed, using a 2:1 randomization ratio, with the strata defined as:

- investigational site,
- SOFA score (<6 versus ≥ 6)

6.3 Study Schedule

The scheduled assessments will be carried out during the study as described in Section 10 of the Study Protocol.

6.4 Study Duration and Early Termination

6.4.1 Patient Discontinuation Criteria

Refer to Section 11.1 of the Study Protocol

6.4.2 Study Completion

Refer to Section 11.2 of the Study Protocol

6.4.3 Duration of Treatment (Days 1-5)

Refer to Section 11.3 of the Study Protocol.

6.4.4 Duration of Study Period (Days 6-28)

Refer to Section 11.4 of the Study Protocol.

6.4.5 Duration of Follow-up (up to 30 days following end of study visit)

Refer to Section 11.5 of the Study Protocol.

6.5 Study Drug Administration

Refer to Section 7.1 of the Study Protocol.

6.6 Study Assessments

6.6.1 Safety Evaluations

Safety evaluations and definitions are described in Sections 8, 10, and 10.1 of the Study Protocol.

6.6.2 Efficacy Evaluations

Efficacy evaluations are described in Section 10.2 of the Study Protocol.

7 Statistical Analysis Methods

7.1 General Considerations

All safety analyses will be based on Safety Population; all efficacy analyses will be based on Modified Intent-to-Treat population, unless otherwise specified. Some specific sensitivity analyses of efficacy may be based on ITT and Per Protocol populations (for primary endpoints only). See Section 7.4 below for definitions of each analysis population.

All analyses will be considered as descriptive analyses. Derivation of two-sided 95% confidence intervals and p-values will be generated where applicable.

Time to event endpoints will be defined as the start date/time to the end date/time; censoring dates will be the last date/time the patient was determined to be event-free. Kaplan Meier methods will be used for time to event endpoint analyses; a log-rank test will be performed to compare the two survival curves. Timepoints estimates and median survival will be derived from the Kaplan Meier analysis. A Cox proportional hazards model may also be used to compare the two treatment arms using a hazard ratio.

Categorical endpoints will be calculated as the percentage of patients with the event, relative to the number of patients in a given analysis population (see Section 7.4). Stratified logistic regression approaches and/or repeated measures statistical approaches may be used to compare patients on the sargramostim and control arms, in addition to Fisher's Exact or Chi² tests (as appropriate). The randomization stratification factor for the baseline SOFA score (<6 versus \geq 6) will be considered for any stratified analysis.

Continuous endpoints will be summarized by n, means, medians, minimum, maximum, and 25th and 75th percentiles. Analysis of variance, analysis of covariance, and/or repeated measures statistical approaches may be used to compare patients on the sargramostim and control arms.

In the event that the underlying assumptions and/or distributions for a given statistical method are not satisfied, alternative statistical methods will be employed.

Additional exploratory analyses may be performed to evaluate the robustness and sensitivity of the study results, including but not limited to, additional evaluation of endpoints on other

analysis populations, subgroup analyses, treatment interactions, adjusted or stratified analyses, and/or alternative statistical methods.

7.1.1 Study Day

Study day will be calculated as follows:

- For the sargramostim arm: Assessments/events prior to the first sargramostim dose date, study day will be the assessment date minus the first dose date. The end of treatment is the date/time of the last administered dose of sargramostim.
- For the control arm, the randomization date will be used as the first dose date. The treatment completion or discontinuation date/time from the treatment disposition CRF page will be considered the end of treatment for the SOC arm.
- Assessments/events on or after the first dose date, study day will be the assessment date minus the first dose date plus one.
- The duration of SOC (for both treatment arms) will be based on the start date of randomization, and the end date as latest of 1) any concomitant medication end date with indication "COVID-19", or 2) any end date of procedure with indication "COVID-19", or 3) any end date of transfusion, ventilation or supplemental oxygen.

For assessments captured as an unscheduled visit, if the date of assessment is the same as a date of another visit (e.g., Day 6, Day 14, Day 28, Day 58, Day 90), then the visit label for the unscheduled assessment can be re-assigned to the appropriate visit label (e.g., Day 6, Day 14, Day 28, Day 28, Day 58, Day 90). Other appropriate data handling approaches may be used to ensure data is analyzed in the appropriate timepoint analysis.

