7.1.3 Analysis Period

The main analysis period would be the Treatment Emergent period.

For all treatment emergent adverse events, it is defined as the period from the date of the first dose until the earliest of the following 1) date of Study Day 58; or 2) date of early discontinuation from study, or 3) data cutoff date. However, SAEs will include all the serious adverse events collected after the first dose.

The analysis period used for abnormalities in laboratory evaluations is defined as the period from the date of the first dose until the earliest of the following 1) date of Study Day 90; or 2) date of Early discontinuation from study, or 3) data cutoff date.

Analysis period for efficacy parameters would be the period from the date of the first dose until the earliest of the following 1) Date of Study Day 90; or 2) Date of Early discontinuation from study, or 3) data cutoff date.

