7.4 Analysis Population

The following analysis populations will be used to summarize the results from this study.

- Safety Population includes all patients who received at least one dose of sargramostim and/or SOC based on actual treatment received. Patients who did not receive any study treatment (either sargramostim and/or SOC) will be excluded from Safety Population. All safety analyses will be based on the Safety Population.
- Intent-to-treat Population (ITT) includes all patients who were randomized, and analyzed per the treatment arm as randomized. Selected efficacy analysis (P(A-a)O₂ and intubation rate) may also be performed based on ITT population for the purpose of sensitivity, unless otherwise specified.
- Modified Intent-to-treat Population (MITT): a subset of the ITT population that received at least one dose of any study treatment (either sargramostim and/or SOC). Efficacy analyses will be based on the MITT Population.
- **Per Protocol Population (PP)** includes all patients who were randomized and received at least one dose of sargramostim and/or standard of care based on the treatment assigned

at randomization and meet the eligibility criteria of this study. Selected efficacy analyses may also be performed based on the Per Protocol Population, unless otherwise specified.

- If the ITT, and PP populations are identical, or less than 10% different compared to the MITT population, then the selected efficacy analyses may not be repeated across the ITT and PP analysis population.
- Enrolled Population includes all patients who were eligible and signed informed consent form (ICF).

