7.11.1.2 Rate of Intubation, and any other Respiratory Support

Another key primary endpoint will be the rate of intubation by Day 14. That is, any occurrence of intubation (mechanical ventilation, or ECMO) at any point time in time between Days 1 and

14, will be considered to be an event. In addition, any intubation at any point during the study will be tabulated. The treatment arms will be compared using a Fisher's Exact or Chi2 test.

Furthermore, the various types of respiratory support will be summarized as specified below, including invasive ventilation (ventilator or ECMO), non-invasive ventilation by CPAP or BiPAP, high flow oxygen, low flow oxygen or no oxygen support required.

The durations of respiratory support (days) are defined as:

Duration of respiratory support

$$= \sum_{k_i=0}^{N_i} (\text{End Date/time on Day } k_i - \text{ Start Date/time on Day} k_i)/24$$

Where, N_i is the total number of available study days for any patient *i*. Respiratory support includes invasive ventilation, non-invasive ventilation and supplemental oxygen. Duration of oxygen support will be summarized by treatment arm; p-values generated from t-tests will compare the differences in the mean values between two treatment arms. These analyses will be generated for any oxygenation support, and for invasive ventilation separately.

Status of requiring respiratory support of each patient, including durations of any respiratory support (by type) will be listed.

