7.12.1 Adverse Event

All adverse events will be coded using Medical Dictionary for Regulatory Activities (MedDRA) version 23.0 (or later). Adverse events will be categorized as prior events, treatment emergent adverse events, and post treatment adverse events:

- Prior Events includes all adverse events with a start date before the first dose of the study drug regardless of the end date.
- Treatment-emergent adverse events (TEAE) are defined as adverse events with a start date (or date of worsening) on or after the first dose of the study drug and no later than the earliest of the following 1) the date for the Day 58; 2) date of early discontinuation from study, or 3) data cutoff date.
- All adverse event started after study day 58 will be considered post-treatment.

All TEAE will be summarized by treatment arm and presented by:

- 1) system organ classification and preferred term (PT);
- 2) PT;
- 3) system organ classification, PT and the maximum severity.

Treatment-related TEAE, serious TEAE and treatment-related serious TEAE will be summarized by MedDRA System Organ Class and PT, and the maximum severity. SAEs and deaths will be listed by patient.

For patients at sites where Aerogen devices were supplied by PTX, the following analyses will be performed:

- All device-related TEAEs will be summarized by treatment arm;
- All device-related TE-SAEs will be summarized by treatment arm;
- All device-related AEs will be listed by patient.

The frequency of treatment-emergent serious adverse events (TESAEs) will be summarized by arm, SOC, and preferred term. Severity (using CTCAE) and relationship of TEAEs to treatment (sargramostim, sargramostim inhalation device or standard of care) will be analyzed as recorded on eCRF (also refer to Section 8 of the Study Protocol for definitions).

Clinically significant adverse drug reactions (ADRs) are treatment-emergent drug-related AEs and SAEs (as discussed above).

If a patient experiences more than one TEAE within a preferred term, the patient will be counted only once in the calculation of incidence of TEAE within that preferred term. Similarly, if a

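### Day 1 is the first dose date in the sargramostim arm but the randomization date in the control arm, so the Day 1–14 intubation endpoint covers different time since randomization in the two arms

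*SAP*

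**What the plan says.** SAP 7.1.1 sets the study-day origin by arm. In the sargramostim arm it is the first sargramostim dose date, and earlier dates get negative values: "Assessments/events prior to the first sargramostim dose date, study day will be the assessment date minus the first dose date". In the other arm: "For the control arm, the randomization date will be used as the first dose date". From the origin onward: "Assessments/events on or after the first dose date, study day will be the assessment date minus the first dose date plus one".

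SAP 7.1.3 starts the efficacy window at the same point: "Analysis period for efficacy parameters would be the period from the date of the first dose until the earliest of the following" (Study Day 90, early discontinuation or data cutoff). SAP 7.11.1.2 defines the primary intubation event as "any occurrence of intubation (mechanical ventilation, or ECMO) at any point time in time between Days 1 and" 14.

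SAP 7.4 defines MITT, the main efficacy population, as the randomized patients who "received at least one dose of any study treatment (either sargramostim and/or SOC"). A patient randomized to sargramostim who received only SOC therefore stays in the analysis.

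Elsewhere the SAP uses randomization for both arms: as the cut for baseline (7.1.2) and as the start of hospitalization duration (7.11.2.5) and SOC duration (7.1.1). For survival, 7.1 speaks only of a start date/time, and 7.11.2.2 gives censoring rules but no origin.

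**The concern.** In a randomized comparison the clock should start at the same event in both arms, and that event is randomization. Here, time between randomization and first inhalation is at risk and counted for controls, but at risk and not counted for sargramostim patients. MITT does not remove the affected patients: someone receiving SOC who is intubated before the dosing date remains in the denominator without contributing an event. If never dosed, that patient has no Study Day, Day 14 or efficacy period, and no fallback is given.

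At stake is the intubation rate by Day 14, one of two primary measures, which 7.11.1.2 compares by Fisher's exact or chi-square test. Mortality and survival time are exposed too if their unstated origin is taken from 7.1.3.

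**Working it through.** The SAP gives no intubation rate, dosing delay or power calculation, so there is no planned figure to reproduce. The check has two parts.

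**1. The dating rule.** Take an event on the randomization date, with the first dose g calendar dates later.

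| g | Control study day | Sargramostim study day | Sargramostim Day 14, counted from randomization date as day 1 |
|---|---|---|---|
| 0 | 1 | 1 | 14 |
| 1 | 1 | -1 | 15 |
| 2 | 1 | -2 | 16 |

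With g = 0 the arms agree. With g ≥ 1 the sargramostim window loses its first g dates and gains g dates at the end. It is shifted, not only shortened.

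**2. Illustrative size.** Assumptions: no treatment effect; 14-day intubation risk of 20% in both arms; all patients kept in the denominators; each intubation dated by its start. Cumulative risk is F(t) = 1 − 0.8^((t/14)^k), a Weibull with shape k, where k = 1 is constant hazard and k < 1 is front-loaded.

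*Exact 1-day gap.* The sargramostim arm counts F(15) − F(1). The control arm counts F(14) = 20%.

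| k | F(1), lost | F(15) | Counted | False difference |
|---|---|---|---|---|
| 1 | 1.58% | 21.26% | 19.68% | -0.32 points |
| 0.7 | 3.46% | 20.88% | 17.42% | -2.58 |
| 0.5 | 5.79% | 20.62% | 14.83% | -5.17 |
| 1.2 | 0.94% | 21.53% | 20.59% | +0.59 |
| 1.5 | 0.43% | 21.92% | 21.50% | +1.50 |

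For k from 1 down to 0.5, the uncounted intubations among 80 sargramostim patients are 80 × 0.0158 ≈ 1.3 to 80 × 0.0579 ≈ 4.6.

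*Calendar-date rule, noon randomization, dosing on the next date.* The control's Day 1 is half a day long, so its window runs from 0 to 13.5 days. The sargramostim window opens at midnight and runs from 0.5 to 14.5 days. False difference = F(14.5) − F(0.5) − F(13.5).

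| k | Sargramostim counted | Control counted | False difference |
|---|---|---|---|
| 1 | 20.64 − 0.79 ≈ 19.84% | 19.36% | +0.48 points |
| 0.7 | 20.44 − 2.14 = 18.30% | 19.55% | -1.25 |
| 0.5 | 20.32 − 4.13 = 16.19% | 19.68% | -3.49 |

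For scale, at 20% in both arms the standard error of the difference is √(0.16/80 + 0.16/40) = √0.006 ≈ 7.7 points.

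**After the change.** With randomization as Day 1 in both arms, both windows cover the same dates from randomization. The false difference is zero for any gap and any shape.

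**The case against.** The strongest reply is that the effect may be absent. Study Day works on dates, so an intubation before inhalation but on the dosing date still counts as Day 1, and same-date dosing loses nothing. The SAP hints that same-date dosing was foreseen: 7.1.2 cuts baseline at the randomization date and adds, for sargramostim, that it must precede the first dose, which adds a restriction only if dosing is on that date or earlier. That is an inference. The SAP does not require same-date dosing, and its timing is left to the protocol.

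Second, a reader might infer that the bias always favours sargramostim. It does not: shapes of 1.2 and 1.5, or a constant hazard with noon randomization, turn the sign. Front-loading is plausible, but nothing in the SAP establishes it.

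Third, a reader might infer that every by-day result is affected. The Up to Day 6 oxygenation value is chosen by last dose plus 24 hours, or in controls by treatment completion or the Day 6 visit (7.1.4), not by Study Day. Baseline and hospitalization duration are tied to randomization.

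Fourth, it is tempting to say that mortality is analysed from first dose. Section 7.11.2.2 names no origin, and its count of deaths has no lower bound. The defect there is an unstated origin.

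Fifth, 7.11.1.2 also tabulates intubation at any point in the study, which could recover early events, and 7.1 and 7.2 call all analyses descriptive. The first is a supplementary table, not the Day 14 endpoint. The second does not make a rate comparable between arms, and p-values are still produced. The optional ITT analysis (7.4, 7.11.1.3) would use the same Study Day rule.

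**Conclusion.** The rule is wrong as written for a randomized comparison of intubation by Day 14, and it leaves never-dosed sargramostim-arm patients in MITT without a Day 1. For survival time the SAP should state an origin, because taking it from 7.1.3 would import the same asymmetry.

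The size cannot be fixed from the SAP. Under the assumed 20% risk, a 1-day gap and constant to front-loaded hazards, the false difference runs from about -0.3 to -5.2 points. Under noon randomization with next-date dosing it runs from about +0.5 to -3.5. Hazards that rise over time move it against sargramostim, and universal same-date dosing makes it nil. All these values are below one standard error of the difference (7.7 points), but they are systematic and avoidable.

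**What to change.** In 7.1.1, 7.1.3, 7.11.1.2 and 7.11.2.2, state that for between-arm efficacy endpoints (intubation by Day 14, mortality and survival time) Day 1 and the time origin are the randomization date in both arms, including patients randomized to sargramostim who were never dosed with it. Keep the first dose as the origin for sargramostim exposure summaries. The treatment-emergent definition in 7.12.1 is not part of this change.

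The cost is SAP wording and programming. The randomization date is already used for both arms in 7.1.2 and 7.11.2.5, so no new data are needed. If every patient was dosed on the randomization date, no dosed patient's Study Day changes.

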7.1.2 Baseline Definition

For both treatment arms, baseline is considered any observation that occurs prior to, or on the date of randomization, unless otherwise specified. That is, baseline date \leq randomization date.

Additionally, for the sargramostim arm, baseline assessments must also be prior to the first sargramostim dose date/time.

If there are multiple baseline assessments, the latest one will be used for analysis purposes.

For assessments on the day of first dose where time is not captured, a nominal pre-dose indicator, if available, will serve as sufficient evidence that the assessment occurred prior to first dose.

Assessments on the day of the first dose where neither time nor a nominal pre-dose indicator are captured, will be considered prior to the first dose if such procedures are required by the protocol to be conducted before the first dose.

In all summaries, change from baseline variables will be calculated as the post-treatment value minus the value at baseline. The % change from baseline will be calculated as (post-baseline value - baseline value) / baseline value x 100.

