7.11.1 Primary Efficacy Evaluations

For primary efficacy measures based on oxygenation parameters, the main timepoints of interest for analyses are baseline, up to Day 6 for P(A-a)O₂ gradient, and by Day 14 for rate of intubation, where data are available, unless otherwise specified.

See Sections 7.1.2, 7.1.3, and 7.1.4 for algorithm on determining assessments to be used for analysis.

As ABG was required only at baseline and at Day 6/Post-Treatment visit (or day of discharge if earlier), the number of patients with complete data at all study visit days is expected to quite limited. Therefore, the primary timepoint for analyses for data based on ABG will be up to Day 6.

7.11.1.1 Oxygenation Up to Day 6

The $P(A-a)O_2$ gradient will be derived using arterial blood gas assessment via arterial puncture at baseline and up to Day 6, or day of discharge whichever is earlier. See Sections 7.1.2, 7.1.3, and 7.1.4 for algorithm on determining assessments to be used for analysis.

The change from baseline and percentage from baseline is defined as:

Percentage Change from Baseline= Change from Baseline/ Baseline

The P(A-a)O₂ gradient, the percent change from baseline up to Day 6 will be tabulated based on "unchanged or deteriorated" [no difference or positive percent change from baseline] and "improved" [negative percent changer from baseline] by 10% change increments. In addition,

the percentage of patients with $a \ge 33\%$ improvement for each treatment arm will be provided. For both of these analyses, a Chi-square, or Fisher's exact test (or stratified logistic model) will be generated to compare the treatment arms. Alternative cutoffs for defining meaningful improvement may be used (e.g., 25%, 50%), with similar analyses methods as above.

The maximum change from baseline and maximum percentage change from baseline will be summarized up to Day 6, and for the study duration.

Maximum percentage change from baseline is defined as:

Maximum Percentage Change from Baseline= Maximum Change from Baseline/ Baseline

For these analyses, the baseline is defined as the last available assessment prior to administration of study drug (see Section 7.1.2 above). Except as noted in Section 7.1.1, unscheduled records will be excluded from the summaries at specific timepoints but will be included in the maximum change from baseline.

A listing of all P(A-a)O₂ gradient measurements will be provided.

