7.11.2.1 Change in Ordinal Scale

Ordinal scale will be assessed at the Screening/Baseline, during the 5 days of treatment administration, and at any days where the patients are hospitalized through Day 28 and at Day 90. Baseline for the following analyses is defined as the last ordinal scale prior to administration of study drug. The number of patients with an improvement in the ordinal scale, defined as a change from baseline of ≥ 2 points, will be tabulated.

A MMRM model will be used to evaluate the change in ordinal scale, in which the change of ordinal scale from baseline on each timepoint of interest will be included as dependent variable and treatment, timepoint (categorical), and treatment-by-timepoint as fixed effects, patient as random effect, and the baseline value as a continuous covariate. An unstructured covariance matrix will be used for the MMRM analysis, unless the model does not converge, in which case the compound symmetry will be used.

Descriptive statistics for the overall treatment effect based on the MMRM model will include the least-squares (LS) mean difference, LS mean change from baseline for each treatment arm, their corresponding 95% CIs, and the p-values associated with the treatment difference compared to SOC. In addition, LS Means for the treatment differences at each timepoint of interest between treatment arms may also be provided with the same set of statistics derived from the same MMRM model defined above based on the MMRM estimates.

Additionally, the non-model based descriptive statistics for the corresponding change from baseline (overall) in the ordinal scale at each visit or timepoint of interest, change from baseline and maximum change from baseline will be evaluated and summarized by treatment arm. Except as noted in Section 7.1.1, unscheduled records will be excluded from the summaries at specific timepoints but will be included in the maximum change from baseline.

All available values of the ordinal scale, including change from baseline and maximum change from baseline will be listed by arm and patient. Refer to Appendix C of the Study Protocol for the ordinal scale categories.

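### Section 7.1.2 gives the sargramostim arm a clock-time cut-off for baseline but controls only a calendar-date cut-off, and later sections restate the rule inconsistently

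*SAP*

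**What the plan says.** Section 7.1.2 opens with a rule for both arms: "baseline is considered any observation that occurs prior to, or on the date of randomization", unless otherwise specified. It adds a condition for one arm: "for the sargramostim arm, baseline assessments must also be prior to the first sargramostim dose date/time". Where several values qualify, "If there are multiple baseline assessments, the latest one will be used for analysis purposes".

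Section 7.1.1 supplies a stand-in for the missing first dose in controls: "For the control arm, the randomization date will be used as the first dose date". This is a date without a time. The same section numbers the days: "Assessments/events on or after the first dose date, study day will be the assessment date minus the first dose date plus one". A control's randomization date is therefore Study Day 1, and Section 7.1.3 starts the efficacy period on the first dose date.

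For the primary gradient analysis, Section 7.11.1.1 restates the rule: "the baseline is defined as the last available assessment prior to administration of study drug (see Section 7.1.2 above"). For the ordinal scale, Section 7.11.2.1 says: "Baseline for the following analyses is defined as the last ordinal scale prior to administration of study drug", with no pointer to 7.1.2. Sections 7.12.2 (laboratory data) and 7.12.4 (vital signs) use similar study-drug wording and do point back to 7.1.2.

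**The concern.** Baseline does several jobs in this plan. It is subtracted in every change score. It is the denominator of the percent change and hence of the responder rate at 33% improvement. It is also the covariate in the mixed models for the gradient and the ordinal scale. The arms are comparable on it only if the same rule picks it in both.

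Here the cut-off is a clock time in one arm and the end of a calendar day in the other. Because the latest eligible value wins, a control with a second reading later on the randomization day has that reading as baseline, after some hours of post-randomization care. In the sargramostim arm, a reading at the same hour is excluded if dosing has begun. The trial is open-label, so staff may know the allocation when a later same-day reading is taken.

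The restatements add a reproducibility problem. Two programmers following different sections could select different values for the same patient.

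**Working it through.** The SAP states no figure on this point, and Section 7.2 says the sample size was not derived from statistical assumptions. There is no planned result to reproduce. The check is to apply the written rules to the same readings.

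**Inputs from the SAP**
- 7.1.2, both arms: date on or before the randomization date, latest value taken.
- 7.1.2, sargramostim only: also before the first dose date and time.
- 7.11.1.1 and similar sections: last value before study drug.
- 7.1.1, controls: randomization date stands in for first dose date, no time.

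**Assumed timelines** (illustrative; randomization at 10:00 on day D0, the following day is D1)

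| Patient | Readings | 7.1.2 selects | Study-drug wording selects |
|---|---|---|---|
| (a) Control | 08:00 and 20:00 on D0 | 20:00 on D0 | 08:00 if the randomization time is used as anchor; none if strictly before the randomization date |
| (b) Sargramostim, first dose 12:00 on D0 | 08:00 and 20:00 on D0 | 08:00 on D0 | 08:00 on D0 |
| (c) Sargramostim, first dose 09:00 on D1 | 08:00 and 20:00 on D0, 07:00 on D1 | 20:00 on D0 | 07:00 on D1 |

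- (a) against (b): identical D0 readings give different baselines by arm under 7.1.2. The control's baseline lies 20 − 10 = 10 hours after randomization.
- In (b), a reading between 10:00 and 12:00 would also qualify. Values after randomization but before dosing are thus allowed in both arms; what differs is the treatment of values after treatment start.
- (a) and (c): the two wordings select different values for the same patient. Case (c) needs both a first dose after the randomization date and a reading between the end of that date and the dose.

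**Size, by assumption only.** Let f be the share of controls with a later same-day reading and b the later value minus the earlier one, in mmHg. The control mean baseline moves by f × b and the mean raw change score by −f × b.

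| f | \|b\| = 5 | \|b\| = 10 | \|b\| = 20 |
|---|---|---|---|
| 0.05 | 0.25 | 0.5 | 1.0 |
| 0.10 | 0.5 | 1.0 | 2.0 |
| 0.25 | 1.25 | 2.5 | 5.0 |
| 0.50 | 2.5 | 5.0 | 10.0 |

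The entries are absolute shifts in mmHg; neither f nor b comes from the SAP. If the gradient has fallen by the later reading (b negative), the control change looks less favourable; if it has risen, more favourable. In the mixed model, which adjusts for baseline, a baseline shift of d moves the adjusted contrast by slope × d, which is less than d in size when the slope lies between 0 and 1.

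**The case against.** The strongest reply is that the SAP has one rule, stated in 7.1.2, and that the later sentences are shorthand for it. Sections 7.11.1.1, 7.12.2 and 7.12.4 all point back to 7.1.2; only 7.11.2.1 does not. This stands to a large extent. A reader might infer two rival definitions for the primary endpoint, but the cross-reference argues against that, and drafting conflict is the better description. It does not remove the problem, because 7.1.2 itself contains the asymmetry and is the section pointed to.

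Three other strong readings are tempting and the document does not support them.

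- That post-randomization care enters baseline in controls only. Section 7.1.2 also admits a sargramostim value taken on the randomization date after randomization but before dosing.
- That a control's baseline doubles as a Day 1 value with zero change by construction. No rule reuses the baseline record as a post-baseline value, and a Study Day 1 label does not make it one. A sargramostim pre-dose value on the first dose date carries the same label. The SAP does not exclude the reuse either, so a sentence excluding it is worthwhile.
- That the two wordings diverge whenever dosing starts the next day. They diverge only if another assessment falls in the gap, and the SAP does not say how often next-day dosing occurs.

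It is also fair to say that exposure of the primary endpoint is limited. Section 7.11.1 says that ABG was required only at baseline and the Day 6 visit, or discharge if earlier, so a second same-day control ABG would be an extra. Nor are controls wholly without an anchor, since 7.1.1 gives a surrogate date. What they lack is a time.

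**Conclusion.** The asymmetry in Section 7.1.2 is real and survives these objections: a stated rule can select a value after the start of the comparison period as baseline for controls, and cannot do so after treatment start for sargramostim. The restatements elsewhere are a secondary drafting conflict.

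The effect on the gradient is probably small, given the ABG schedule. The ordinal scale and SpO₂/FiO₂ may be more exposed if recorded more often on the randomization day. The SAP gives nothing from which to estimate the size, and the range of 0.25 to 10 mmHg above only illustrates the arithmetic. All analyses are declared descriptive, so the harm is possible bias and poor reproducibility of the estimates, intervals and p-values, not loss of type I error control. The point should be corrected, but it does not by itself undermine the trial.

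**What to change.** Put one rule in Section 7.1.2 for both arms and all endpoints:

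- Baseline is the last value at or before the date and time of randomization.
- If the time is missing, use the value labelled screening or baseline.
- Later values on the randomization date are not baseline, in either arm.
- The record selected as baseline is never also used as a Day 1 post-baseline value.

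Replace the study-drug sentences in 7.11.1.1, 7.11.2.1, 7.12.2 and 7.12.4 with a plain reference to this rule.

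The cost is SAP wording only, to be settled before database lock. A few sargramostim baselines will be slightly earlier relative to the first dose than under the current text. That is a small price for the same cut-off in both arms.
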